## 8.2. Secondary Endpoints

### 8.2.1. Key Secondary Endpoint

The Key Secondary Endpoint of HLA alloimmunization will be compared between the two groups using Fisher's exact test with a 2-sided test at the 0.05 level of significance. Blood System Research Institute will assume all analytic responsibilities of the Key Secondary Efficacy Endpoint for safety, interim and final analysis and details of this analysis are provided in Appendix II generated by BSRI.

### 8.2.2. Additional Secondary Endpoints

The additional secondary study endpoints and their corresponding analyses are discussed in detail below. All Secondary Endpoints will be compared based on study arm, (MIRASOL vs CONTROL), using the mITT set. Each of the ten additional Secondary Endpoints, as well as their respective analytic approaches is discussed as follows:

#### 1. Proportion of subjects with $\geq$ grade 2 bleeding.

For each study arm, the proportion of subjects with at least 1 day of grade 2 or higher bleeding Day 0 through Day 27 (or until transfusion independence is achieved) will be calculated, where,  $p_t$  denotes the proportion of the MIRASOL group and  $p_c$  denotes the proportion for the CONTROL group.  $p_t$  and  $p_c$  will be calculated using the equations below:

$$p_T = \frac{\text{Number of Subjects with } \geq \text{ grade 2 Bleeding (Test Arm per mITT)}}{\text{Total Number of Subjects in the Test Arm per mITT}}$$

$$p_C = \frac{\text{Number of Subjects with } \geq \text{ grade 2 Bleeding (Control Arm per mITT)}}{\text{Total Number of Subjects in the Control Arm per mITT}}$$

The difference between the MIRASOL and CONTROL arms ( $p_T - p_C$ ) will be reported along with the 95% CI about this difference. The 95% CI and the corresponding p-value will be generated using Fisher's exact test to test the superiority null hypothesis of  $p/p_c=1$ . Negative values of the reported difference favor the MIRASOL group.

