### **7.4.1. Dropouts and Missing Data**

Handling of subject dropouts and other forms of missing data with regard to the primary endpoint will be discussed in Section 8.1. Handling of subject dropouts and other forms of missing data with regard to key secondary endpoints is the responsibility of BSRI. No imputation of missing data will be applied to secondary, exploratory or safety endpoints unless otherwise specified.

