### **7.5.2. Modified Intent-to-Treat Analysis Set**

The mITT analysis set is defined as containing all randomized subjects who undergo at least one (1) study transfusion post-randomization based on the treatment group to which they were randomized. Subjects will be analyzed according to the treatment group (MIRASOL or CONTROL) they were assigned at randomization.

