Results of the primary analysis will be displayed by treatment group and will include the average number of grade 2 or higher bleeds (including minimum and maximum), the average duration of on-protocol days or days of transfusion dependence (including minimum and maximum), the estimate of the mean rate, the natural logarithm of the estimate of the mean rate and the corresponding 95% CIs. The value of the point estimate, i.e.  $\ln(\lambda_T) - \ln(\lambda_C)$ , and its corresponding 95% CI will also be displayed.

An NI analysis will also be carried out to assess the secondary efficacy endpoint of proportion of subjects with  $\geq$  grade 2 bleeding (Section 8.2.2 below). We let  $p_i$  and  $p_c$  represent the probability of a patient experiencing WHO  $\geq$  grade 2 or higher bleeding in the MIR or CONTROL arm, respectively. With an NI margin of 1.2, the null hypothesis is  $H_0: p_i/p_c > 1.2$  (MIR has more than a 20% higher probability of a patient experiencing at least one WHO  $\geq$  grade 2 bleed compared to CONTROL). The alternative hypothesis is  $H_A: p_i/p_c \leq 1.2$  (MIR has no more than a 20% higher relative bleeding rate compared to CONTROL). The risk difference will be calculated using the Wald Test.

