#### 2. Time to first grade 2 or higher bleed

The time to first grade 2 or higher bleeding will be analyzed using a log rank test comparing survival curves stratified by treatment group. The timeframe under consideration is defined from the day of the subject's first post randomization PLT transfusion to the day the subject experiences their first grade 2 or higher bleed. Subjects that do not experience a grade 2 or higher bleed will be censored at Day 27 or at date of transfusion independence (10th day without a PLT transfusion prior last follow-up day or Day 27 whichever is earlier), where appropriate. Subjects that do not complete the study or are lost to follow-up will be censored on the date of their last study visit in the treatment period. A Kaplan-Meier (KM) plot contrasting the two study arms will also be generated to provide a visual representation of probability of remaining free of a WHO grade 2 or higher bleed as a function of time since first post-randomization transfusion.

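### The proportions with grade 2+ and grade 3+ bleeding have no follow-up rule, so withdrawal before a bleed counts as bleed-free and unequal withdrawal biases the 1.2 non-inferiority comparison

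*SAP*

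**What the plan says.** SAP 8.2.2 item 1 defines the endpoint as "the proportion of subjects with at least 1 day of grade 2 or higher bleeding Day 0 through Day 27 (or until transfusion independence is" reached). The MIRASOL denominator is the "Total Number of Subjects in the Test Arm per mITT", and CONTROL is handled the same way. The mITT set in 7.5.2 is "all randomized subjects who undergo at least one (1) study transfusion post-randomization", with no requirement on follow-up. Section 7.4.1 adds: "No imputation of missing data will be applied to secondary, exploratory or safety endpoints unless otherwise specified". Item 1 specifies no exception. Item 3 (grade 3 or higher) is analysed identically.

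Item 1 also has a non-inferiority comparison in 8.1.3: "An NI analysis will also be carried out to assess the secondary efficacy endpoint of proportion of subjects with" grade 2 or higher bleeding. The margin is a ratio: "With an NI margin of 1.2, the null hypothesis is" that the MIRASOL-to-CONTROL ratio exceeds it. The only method named is for a difference: "The risk difference will be calculated using the Wald Test". No alpha or confidence level is given for this comparison.

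Two other analyses do allow for shorter follow-up. The primary analysis (8.1.1) uses the log of assessed days as an offset. For time to first bleed, 8.2.2 item 2 has this rule: "Subjects that do not complete the study or are lost to follow-up will be censored on the date of their last study visit".

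**The concern.** A subject who withdraws on Day 3 without a bleed stays in the denominator, adds nothing to the numerator, and looks the same as a subject observed bleed-free for all 28 days. Bleeds that would have occurred after withdrawal are therefore counted as absent.

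If MIRASOL loses more subjects this way than CONTROL, its proportion is pulled down further and the ratio falls relative to its true value. In a non-inferiority comparison that is the anti-conservative direction. At stake is any statement that MIRASOL meets the 1.2 margin for the proportion of subjects who bleed. The grade 3 or higher comparison has the same weakness, although the plan gives it no explicit margin.

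**Working it through.** **The plan's own figures.** No sample size or power is given for the 1.2 comparison. The 85% power in 6.3.3 belongs to the primary endpoint (margin 1.6), so there is no planned figure to reproduce here.

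**Inputs**
- From the SAP: 558 mITT subjects randomized 1:1, so 279 per arm (6.3.3); ratio margin 1.2 (8.1.3).
- Assumed, because the documents are silent: a Wald test on the log risk ratio at one-sided 0.025; control proportion p_C from 0.3 to 0.7; withdrawal of 5% to 20% per arm after first transfusion. The 10% in 6.3.3 covers only subjects who are never transfused.
- Assumed timing: constant bleeding and withdrawal hazards over 28 days, with withdrawal unrelated to bleeding risk.
- The true ratio is set at the margin: p_T = 1.2 × p_C. The false non-inferiority rate should then be about 0.025.

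**Step 1: what the crude proportion estimates.** With true 28-day risk p and withdrawal probability w, the expected crude proportion is

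ln(1−p) / [ln(1−p) + ln(1−w)] × [1 − (1−p)(1−w)].

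Take p_C = 0.5, with 15% withdrawal on MIRASOL and 5% on CONTROL:
- MIRASOL (p = 0.60): 0.916/(0.916 + 0.163) × (1 − 0.40 × 0.85) = 0.849 × 0.66 = 0.561
- CONTROL (p = 0.50): 0.693/(0.693 + 0.051) × (1 − 0.50 × 0.95) = 0.931 × 0.525 = 0.489
- Observed ratio: 0.561/0.489 = 1.147, against a true 1.2

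**Step 2: effect on the test.** SE(log ratio) = √[0.439/(279 × 0.561) + 0.511/(279 × 0.489)] = 0.081. The chance that the upper limit falls below ln 1.2 is Φ[(0.182 − 0.137)/0.081 − 1.96] = Φ(−1.40) = 0.081. Simulation of 40,000 trials gives 0.084. Simulated results for all cases:

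| Withdrawal, MIRASOL / CONTROL | Observed ratio at p_C 0.3 / 0.5 / 0.7 | False non-inferiority rate at p_C 0.3 / 0.5 / 0.7 |
|---|---|---|
| 10% / 10% | 1.20 / 1.20 / 1.21 | 0.027 / 0.026 / 0.021 |
| 10% / 5% | 1.17 / 1.17 / 1.18 | 0.042 / 0.045 / 0.053 |
| 15% / 5% | 1.14 / 1.15 / 1.16 | 0.059 / 0.084 / 0.112 |
| 20% / 5% | 1.11 / 1.12 / 1.13 | 0.087 / 0.141 / 0.204 |
| 5% / 15% | 1.26 / 1.26 / 1.26 | 0.009 / 0.005 / 0.003 |

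**Step 3: loss concentrated early.** Suppose 15% of MIRASOL and 5% of CONTROL leave bleed-free with 80% of their arm's 28-day risk still ahead. At p_C = 0.5 the crude proportions are 0.60 − 0.15 × 0.48 = 0.528 and 0.50 − 0.05 × 0.40 = 0.48, so the ratio is 1.10. SE = √[0.472/(279 × 0.528) + 0.52/(279 × 0.48)] = 0.084, and the rate is Φ[(0.182 − 0.095)/0.084 − 1.96] = 0.18. The ratio is 1.10 at any p_C, because 1.2 × 0.88/0.96 = 1.10. With SE 0.129 at p_C = 0.3 and 0.055 at p_C = 0.7, the same formula gives about 0.10 and 0.35.

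**Step 4: how many subjects it takes.** About 4 net missed bleeders among 279 MIRASOL subjects double the rate to 0.05. About 8 to 9 take it to 0.10. About 23 to 25 are needed before a false non-inferiority finding is as likely as not.

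**Step 5: censoring withdrawals.** When the same model is analysed with withdrawals censored, the simulated ratio returns to 1.20 and the false non-inferiority rate to 0.02 to 0.03 across the unequal-withdrawal cases.

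**Step 6: deaths.** Fatal bleeding is grade 4 in Appendix I, so it already counts as a bleed. A death from another cause before any bleed is a non-event in the crude proportion, and it is also a non-event in a cumulative incidence with death as a competing event. With deaths and no withdrawals, the two estimates were the same in simulation (0.5621 and 0.5621).

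**The case against.** **Status.** Section 7.4 reserves formal testing for the primary outcome and calls secondary outcomes supportive and exploratory. Section 7.4.4 applies no multiplicity adjustment to them. A reader might infer that the trial's non-inferiority claim is at risk. The documents do not support that: the primary analysis uses the offset and is not touched by this counting rule. This objection stands and limits the weight of the point.

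**Existing check.** Time to first bleed already censors early leavers, so differential loss could show as a discrepancy between items 1 and 2. This stands in part. Item 2 has a log-rank test but no 1.2 margin, it also censors at transfusion independence, and grade 3 or higher bleeding has no such companion analysis.

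**Direction and size.** Nothing in the documents predicts more withdrawal on MIRASOL, so it would be wrong to infer that the rule always favours MIRASOL. The 0.18 result depends on early loss and one control proportion, so it is neither a central value nor a ceiling.

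**Deaths.** A reader might infer that early deaths are miscounted and that a competing-risk analysis would correct this. Step 6 shows that it would not. How to count such deaths is a choice that the plan should state; it is not an error that the estimator removes.

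**The remedy's own assumption.** Censoring is valid only if withdrawal is unrelated to bleeding risk. If it is related, the cumulative incidence is biased too. This stands, and is why the crude proportions should still be reported.

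**Conclusion.** The point holds for withdrawals. Items 1 and 3 score withdrawal before a bleed as bleed-free, and unequal withdrawal biases the comparison with 1.2. With more withdrawal on MIRASOL spread over 28 days, the false non-inferiority rate rises from a nominal 0.025 to about 0.04–0.05 (10% versus 5%), 0.06–0.11 (15% versus 5%) or 0.09–0.20 (20% versus 5%). Early loss at 15% versus 5% gives about 0.18 at a control proportion of 0.5. Equal withdrawal is nearly neutral, and the reverse imbalance is conservative.

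These figures rest on an assumed test, level, control proportion, withdrawal pattern and timing, none of which the documents give. The matter is a worthwhile correction to a supportive endpoint. It is not a threat to the primary conclusion, and it is not a finding about deaths.

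**What to change.** For items 1 and 3 and the margin-1.2 comparison:
- Estimate p_T and p_C as the cumulative incidence, by Day 27, of a first bleed of the stated grade.
- Censor withdrawals at the last assessed day.
- Carry transfusion-independent subjects as bleed-free to Day 27, as 8.1.1 does. Item 2's censoring at transfusion independence should not be copied here.
- Form the ratio and the difference, with confidence intervals, from these estimates. State the scale and confidence level of the 1.2 comparison, since 8.1.3 pairs a ratio margin with a risk-difference method.
- Report the crude mITT proportions alongside.
- State that death from another cause before a bleed is a competing event and remains a non-event. Add a sensitivity analysis with death or bleed as a composite.

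The cost is SAP wording and a short program on bleeding-assessment data already collected. The downsides are slightly wider confidence intervals and the assumption that withdrawal is unrelated to bleeding risk. The rule should be fixed before unblinding, because a choice made after differential loss is seen would be hard to defend.

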#### 2. Time to first grade 2 or higher bleed

The time to first grade 2 or higher bleeding will be analyzed using a log rank test comparing survival curves stratified by treatment group. The timeframe under consideration is defined from the day of the subject's first post randomization PLT transfusion to the day the subject experiences their first grade 2 or higher bleed. Subjects that do not experience a grade 2 or higher bleed will be censored at Day 27 or at date of transfusion independence (10th day without a PLT transfusion prior last follow-up day or Day 27 whichever is earlier), where appropriate. Subjects that do not complete the study or are lost to follow-up will be censored on the date of their last study visit in the treatment period. A Kaplan-Meier (KM) plot contrasting the two study arms will also be generated to provide a visual representation of probability of remaining free of a WHO grade 2 or higher bleed as a function of time since first post-randomization transfusion.

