8.2.2. Additional Secondary Endpoints

The additional secondary study endpoints and their corresponding analyses are discussed in detail below. All Secondary Endpoints will be compared based on study arm, (MIRASOL vs CONTROL), using the mITT set. Each of the ten additional Secondary Endpoints, as well as their respective analytic approaches is discussed as follows:

1. Proportion of subjects with \geq grade 2 bleeding.

For each study arm, the proportion of subjects with at least 1 day of grade 2 or higher bleeding Day 0 through Day 27 (or until transfusion independence is achieved) will be calculated, where, p_t denotes the proportion of the MIRASOL group and p_c denotes the proportion for the CONTROL group. p_t and p_c will be calculated using the equations below:

$$p_T = \frac{\text{Number of Subjects with } \geq \text{ grade 2 Bleeding (Test Arm per mITT)}}{\text{Total Number of Subjects in the Test Arm per mITT}}$$

$$p_C = \frac{\text{Number of Subjects with } \geq \text{ grade 2 Bleeding (Control Arm per mITT)}}{\text{Total Number of Subjects in the Control Arm per mITT}}$$

The difference between the MIRASOL and CONTROL arms ($p_T - p_C$) will be reported along with the 95% CI about this difference. The 95% CI and the corresponding p-value will be generated using Fisher's exact test to test the superiority null hypothesis of $p/p_c=1$. Negative values of the reported difference favor the MIRASOL group.

2. Time to first grade 2 or higher bleed

The time to first grade 2 or higher bleeding will be analyzed using a log rank test comparing survival curves stratified by treatment group. The timeframe under consideration is defined from the day of the subject's first post randomization PLT transfusion to the day the subject experiences their first grade 2 or higher bleed. Subjects that do not experience a grade 2 or higher bleed will be censored at Day 27 or at date of transfusion independence (10th day without a PLT transfusion prior last follow-up day or Day 27 whichever is earlier), where appropriate. Subjects that do not complete the study or are lost to follow-up will be censored on the date of their last study visit in the treatment period. A Kaplan-Meier (KM) plot contrasting the two study arms will also be generated to provide a visual representation of probability of remaining free of a WHO grade 2 or higher bleed as a function of time since first post-randomization transfusion.

3. Proportion of subjects with \geq grade 3 bleeding

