## 7.7. Calculation of Study Day and Treatment Period

The day the subject receives their first post-randomization PLT transfusion will be considered Day 0. If the subject's PLT transfusion episode spans two calendar days, the day the transfusion started will be considered Day 0.

The treatment period is defined as the period of time from Day 0 through Day 27 or to the day of transfusion independence, defined as the last of ten (10) successive days after the last PLT transfusion (on- or off-protocol), whichever occurs first. Bleeding assessments are conducted at baseline and are to be conducted every day from Day 0 until the post-transfusion follow-up visit or early termination visit.

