### 8.1. Primary Endpoint

Bleeding assessments based on the WHO Grading Scale for Bleeding will be conducted at baseline to assess eligibility prior to randomization, as well as daily starting on Day 0 and continuing to the post-transfusion bleeding assessment OR until transfusion independence (the last day of ten [10] consecutive days without a PLT transfusion). Each bleeding assessment will document the WHO Bleeding Scale components observed over the course of the prior calendar day, from 00:00 to 23:59. As such, the analysis of the Primary Endpoint, and Secondary Endpoint #2, will be based on bleeding assessments collected on Day 1 thru Day 28 which represent bleeds which occurred on Days 0-27.

The total number of days with WHO grade 2 or higher bleeding is obtained by counting the total number of calendar days (00:00 to 23:59) on which bleeding was assessed and found to be present. For example, if a subject has WHO grade 2 bleeding on Day 1, grade 2 bleeding on Day 2, and grade 3 bleeding on Day 3, this is considered 3 days of grade 2 or higher bleeding. Hematomas (bruises), petechiae, and purpura

[figure not shown]
(e.g., types of bleeding that occur under the skin) represent unique cases in which they are only counted as additional days of bleeding if they are new or manifest in another anatomical location.

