### 8.1.1. Primary Analysis

The MIRASOL vs CONTROL group will be compared with respect to the number of days of WHO grade 2 or higher bleeding. This will be carried out by fitting a negative binomial regression model with an offset defined as the natural logarithm ( $\ln$ ) of the number of days that bleeding was assessed in order to account for the fact that subjects may have different numbers of bleeding assessment days. As an example, if a subject had bleeding assessed on only 10 of 28 days, an “offset” of  $\ln(10)$  bleeding assessment days is incorporated into the linear predictor of the model. Similarly, if bleeding is assessed on each of the full 28 days of the planned treatment period, an offset of  $\ln(28)$  bleeding assessment days is incorporated. Adjustment using this offset will ensure that bleeding *rates* are calculated and compared between treatment groups and that the variable number of days with bleeding assessments across individuals is appropriately dealt with. Subjects who obtain transfusion independence prior to Day 28 will be assumed to have zero bleeding days between the date of transfusion independence and Day 27 and treated as if they had bleeding assessed on each of those days; these days will therefore contribute to the total number of bleeding assessment days used to calculate the offset. Subjects who drop-out of the study before Day 28 for reasons other than transfusion independence will contribute bleeding data for each of the days bleeding was assessed prior to the time of drop-out; bleeding status will not be simulated beyond the time of drop-out since the use of an appropriately computed offset deals with the variable duration of follow-up.

The handling of data following the administration of an off-protocol transfusion requires discussion. Here an off-protocol transfusion is defined as the transfusion of any kind of PLT product that differs from that to which the subject was randomized (i.e. MIRASOL or CONTROL).

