On occasions where a subject receives a mix of off-protocol and on-protocol units on the same day, they will be considered in an on-protocol period on that day. Transfusions can last more than one calendar day. The daily on- and off-protocol statuses will be assigned for the day the transfusion(s) starts. For subjects whose last transfusion is off-protocol, bleeding will be simulated until the subject completes the transfusion period or reaches transfusion independence. If the subject achieves transfusion independence prior to completing the transfusion period, the rules for transfusion independence will take over and subjects will be assumed to have zero bleeds and full follow-up from the day of transfusion independence until Day 27 inclusive (i.e. the remainder of the transfusion period).

Unless otherwise stated any subsequent analysis herein referring to the primary endpoint method will include the individualized simulated bleeding data for the off-protocol periods of time. This simulation will be done twice. Once at the IA and once at the final analysis. The set of simulations done for the primary efficacy analysis will be used for all subsequent analyses wherein off-protocol intervals are called to use simulated bleeding data.

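### The Kaplan-Meier plot for time to first grade 2 or higher bleed censors at transfusion independence, so under the primary analysis's own zero-bleed assumption it overstates bleeding incidence late in the period

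*SAP*

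**What the plan says.** SAP section 8.2.2, item 2 gives the censoring rule: "Subjects that do not experience a grade 2 or higher bleed will be censored at Day 27 or at date of transfusion independence". Subjects who leave early are censored at their last visit in the treatment period. The endpoint "will be analyzed using a log rank test comparing survival curves stratified by treatment group", and the KM plot is said to show the "probability of remaining free of a WHO grade 2 or higher bleed as a function of time since first post-randomization transfusion". No hazard ratio and no significance level are given for it. Section 8.2.2, item 2 of the Protocol document carries the same rule ("will be censored at Day 27 or at date of transfusion independence").

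SAP section 8.1.1 handles the same subjects differently. Those who reach TI early "will be assumed to have zero bleeding days between the date of transfusion independence and Day 27", and those days count as assessed in the offset. For subjects whose last transfusion was off-protocol, the rule is repeated: they are "assumed to have zero bleeds and full follow-up from the day of transfusion independence until Day 27 inclusive". The interim simulation in section 8.6 makes the same assumption.

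Section 7.7 places TI ten days after the last platelet transfusion: "defined as the last of ten (10) successive days after the last PLT transfusion (on- or off-protocol), whichever occurs first". Neither document explains why the two sections differ, treats TI as a competing event, or plans a cumulative incidence curve.

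**The concern.** KM censoring assumes that a censored subject has the same future risk as those still under observation. The primary analysis assumes that a subject who has reached TI has no further risk up to Day 27. Both cannot be true of the same subjects. If the primary assumption holds, the censoring is informative, and the plotted curve is not the unconditional probability that the SAP says it is. It will also disagree with secondary endpoint 1, which counts the same event over the same period with all mITT subjects in the denominator.

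The log-rank test is affected in a related way. Suppose one product keeps subjects transfusion-dependent for longer. They spend more days at risk, and more of them bleed. A test that removes subjects at TI compares only the daily hazard among those still dependent, so it may give little weight to the extra bleeding.

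**Working it through.** The plan states no design figure for this endpoint, so there is none to reproduce. From the documents: 279 mITT subjects per arm (558, 1:1), the 10-day definition of TI, and zero bleeding after TI. Assumed: the hazards, the timing of TI, and a two-sided 0.05 level.

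**1. Closed form.** Take a hazard of 0.04/day up to TI and TI day D uniform over Days 10 to 28.

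- KM limit at day t: 1 - exp(-0.04t).
- True incidence at day t: the mean over D of 1 - exp(-0.04 min(D, t)).

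| Day | 1-KM | True incidence | Gap (points) |
|---|---|---|---|
| 10 | 33.0% | 33.0% | 0 |
| 14 | 42.9% | 41.8% | 1 |
| 21 | 56.8% | 50.1% | 7 |
| 28 | 67.4% | 52.2% | 15 |

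The gap is zero before Day 10 because TI cannot occur earlier. The Day 28 row is the worst point on the curve. The number still at risk on Day 27 is 279 × (1/18) × exp(-1.08) ≈ 5 per arm.

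**2. Simulated KM bias.** Last-transfusion day L is gamma-distributed with mean 6 in control (a shape of 2 reproduces the 98% who reach TI by Day 27), and TI = L + 10. The daily first-bleed hazard applies up to L. In the ten transfusion-free days before TI (the run-in) it stays the same, is halved, or is zero. After TI it is zero. Each cell shows 1-KM against true incidence at Day 27, control arm.

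| Daily hazard | Run-in same | Run-in halved | Run-in zero |
|---|---|---|---|
| 0.02 | 43% vs 27% | 30% vs 20% | 14% vs 12% |
| 0.04 | 68% vs 46% | 51% vs 35% | 25% vs 22% |
| 0.08 | 90% vs 71% | 76% vs 57% | 42% vs 39% |

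The overstatement appears in every cell and runs from about 2 to 22 points. As a check, at a constant 0.04 the KM limit over 28 days is 1 - 0.96^28 = 68%.

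**3. Log-rank test.** Mean L is 6 in CONTROL and 12 in MIRASOL, with 279 per arm and 1,000 trials per scenario. At 0.04/day:

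| Run-in hazard | True incidence, CONTROL vs MIRASOL | Rejection, censored at TI | Rejection, carried to Day 27 |
|---|---|---|---|
| Same | 46% vs 55% | 5% | 36% |
| Halved | 35% vs 46% | 21% | 67% |
| Zero | 22% vs 36% | 81% | 93% |

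Across hazards 0.02 to 0.08, rejection under the SAP rule is 4-5%, 15-27% and 58-90% in the three rows. Carried to Day 27 it is 24-36%, 51-69% and 79-96%. With equal L in both arms, both rules stay near 5%.

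**The case against.** The rule has a basis in the plan. Sections 6.1 and 7.7 end the treatment period at TI, and section 8.1 describes bleeding assessment as "continuing to the post-transfusion bleeding assessment OR until transfusion independence". Section 7.4.1 rules out imputation for secondary endpoints unless otherwise specified. Censoring where planned observation ends fits all of this, and it keeps the zero-bleed assumption out of a second endpoint. If bleeding continued after TI at the same hazard, KM would be unbiased and the primary rule would be the one in question. A log-rank test during dependence also separates the bleeding hazard from the duration of dependence, which is a legitimate complementary question.

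Most of this stands as a defence of the test. It does not rescue the plot, because section 8.2.2 attaches no such condition to the curve.

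A reader might infer three stronger things that the documents do not support:

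- **That the log-rank test cannot see harm from longer dependence.** This needs a daily hazard that is constant through the ten run-in days. No section says so, and the test keeps power when the hazard falls after the last transfusion. A claim that the hazard ratio stays at 1 refers to a quantity the plan does not estimate for this endpoint.
- **That a 15-point error runs along the whole curve.** That is the endpoint value under one assumed hazard, where almost nobody remains at risk.
- **That a 20% longer dependence raises true incidence from 52.2% to 57.7%.** That scaling also stretches the fixed ten days. Scaling only the transfusion part (1.2 × (D - 10) + 10, capped at 28) gives 54.7%, a difference of 2.5 points.

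Nor would the harm go unnoticed in the trial. The primary rate counts post-TI days in its offset, endpoint 1 uses all mITT subjects, and endpoint 7 analyses the duration of platelet support. Some disagreement between KM and endpoint 1 is expected anyway, since endpoint 1 counts bleed-free dropouts as non-bleeders.

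**Conclusion.** The inconsistency between section 8.2.2, item 2 and section 8.1.1 is real and unexplained. Given the primary analysis's assumption of no bleeding after TI, 1-KM overstates the incidence of a first grade 2 or higher bleed late in the treatment period, and the description of the plot is wrong. The range of about 2 to 22 points at Day 27 rests entirely on assumed hazards and TI times, and a different assumption about bleeding after TI would remove the bias. The TI-censored log-rank test is a valid comparison of hazards during dependence. It misses harm from longer dependence when the hazard is constant up to TI and has reduced power for it otherwise. Section 7.4 treats secondary endpoints as supportive and exploratory, so the consequence is a misleading figure and a test open to misreading, with no effect on the primary conclusion or sample size.

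**What to change.** In section 8.2.2, item 2, replace the KM plot with the cumulative incidence of a first grade 2 or higher bleed, with TI as a competing event and censoring before Day 27 only for dropout. Carrying bleed-free TI subjects as event-free to Day 27, as in section 8.1.1, gives the same curve when there is no dropout. With dropout, the competing-event estimator is the safer of the two, because carried-forward subjects can no longer drop out.

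Keep the TI-censored log-rank test and state that it compares bleeding hazards during transfusion dependence. Add a sentence saying that the incidence curve relies on the same assumption of no bleeding after TI as the primary analysis.

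The cost is a few lines of SAP text and a small programming change (one derived status or date). The drawback is that a second endpoint now leans on that assumption. Retaining the TI-censored test leaves one comparison that does not.
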